2.3 Outcome Measures

Primary objective: Usability and feasibility

- Measures:
 - Self-Efficacy for Appropriate Medication Use Scale
 - Beliefs About Medication questionnaire (at baseline)
 - Satisfaction and acceptance questionnaire

Secondary objective: medication adherence

- Measures, Self-reporting:
 - Morisky Medication Adherence Scale
 - Medication Adherence Questionnaire
 - Brief Medication Questionnaire
 - 7-day recall
- Measures, Objective:
 - Electronic data collected by the KARIE device. Adherence may be calculated as the number of dispensed doses/ the total number of prescribed doses during the prescription period *100

3 Procedures

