3.4 Data Collection

The study RA will contact each study participant to arrange a data collection session within 24-48 hours prior to discharge. Data collection will include those scales identified in Outcome Measures above. Following discharge to the community, RAs will contact study participants via telephone on a bi-weekly basis to enquire about any missed medications. During these telephone contacts the RA and study participant will review the medication adherence log for the previous 2 weeks.

Data collection will be repeated at 3-months post-discharge. The RA will contact the participant 1-2 weeks prior to completion of the 3-month intervention period to schedule in in-home visit where post-intervention data collection will take place. In addition, the RA will collect participant medication adherence log.

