4 ANALYSIS

A 2x2 repeated measures analysis of variance will be conducted to test for significant between-groups differences at baseline and post-intervention, as well as within-groups comparisons from baseline to post-intervention. An intention-to-treat analysis using last-observation-carried-forward will be used to account for subjects who do not complete the 3-month intervention.

We will follow qualitative analysis methods established in healthcare research: simple content analysis of survey results and inductive thematic analysis of interview results. With regard to survey and interview data, we will also conduct descriptive statistics across intervention and control baseline measures to assess the variability within measures, and bivariate association between measures of adherence. Results will be interpreted cautiously rather than considered definitive.

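### For the repeated scales, last-observation-carried-forward enters a pre-discharge score as the 3-month result, and no sensitivity analysis is planned

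*Combined protocol and SAP*

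**What the plan says.** Section 3.4 (Data Collection) gives the scales two occasions. The first is a session "within 24-48 hours prior to discharge", of which it says: "Data collection will include those scales identified in Outcome Measures above". The second is stated as: "Data collection will be repeated at 3-months post-discharge". Between them, "RAs will contact study participants via telephone on a bi-weekly basis to enquire about any missed medications", and the adherence log is reviewed. No scale is scheduled in these calls.

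Section 4 (Analysis) tests the arms at baseline and post-intervention in a 2x2 repeated-measures ANOVA. Its only rule for incomplete participants is: "An intention-to-treat analysis using last-observation-carried-forward will be used to account for subjects who do not complete the 3-month intervention". It gives no other missing-data method, no assumption about why values are missing, and no sensitivity analysis.

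The point covers only scales taken on both occasions. Section 2.3 (Outcome Measures) also lists "Electronic data collected by the KARIE device". Like the log and the calls, the device has values between the two occasions. The beliefs questionnaire is marked as baseline only. All of these are outside the point. The satisfaction and acceptance questionnaire may be outside it too: section 4 does not say whether it enters the ANOVA or the separate track of "simple content analysis of survey results and inductive thematic analysis of interview results".

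**The concern.** With no interim scale score, the only value available to carry forward was recorded before the participant went home. It says nothing about the follow-up period. The group-by-time test in a 2x2 design compares mean change between arms, so each imputed participant pulls that arm's mean change towards zero. If scores drift in both arms for reasons unrelated to the device, the arm that loses more people appears to drift less, and the test can read this as a device effect.

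This ANOVA is the only between-arm test that the plan names. It would serve the self-efficacy scale under the primary objective and the self-report adherence scales under the secondary one. Only one arm has a device to live with, so equal drop-out cannot be taken for granted. Without a sensitivity analysis, a reader of the results could not see how far they depend on the carried-forward scores.

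**Working it through.** **Inputs from the documents.** Two scale occasions (section 3.4); LOCF and the 2x2 ANOVA (section 4); 75 per arm, 80% compliance and 94 per arm (section 2.2, West Park only).

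**Assumptions, because the documents give no figure.** SD 1 at each occasion and correlation 0.5, so the change SD is √(1 + 1 − 2×0.5) = 1; two-sided 5% test; average drop-out 20%, borrowed from the 80% compliance, a term that section 2.2 does not define; the split of drop-out between arms; the change common to both arms.

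**1. The plan's own figure.** 75/0.80 = 93.75, rounded up to 94, as stated. If compliance means completion, 0.20 × 94 = 18.8, so about 19 per arm would carry a score forward.

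**2. Which score is carried.** Section 3.1 has the research assistant take baseline measures at consent. Section 2.1 randomises one week before discharge. The section 3.4 session comes 24 to 48 hours before discharge.
- (a) If the section 3.4 session is the baseline, the imputed change is exactly zero.
- (b) If the consent-time baseline is a separate session, the imputed change is whatever happened between consent and discharge.

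Neither contains any follow-up information. The steps below use (a).

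**3. Formula.** Let drop-out in an arm be p, unrelated to baseline or outcome, and let the common mean change be d. Under LOCF the arm's mean change is (1−p)d and its variance is (1−p)(1+d²) − [(1−p)d]². With no true effect, the difference SME+K minus SME is −d(p_K − p_S). It is zero if either factor is zero.

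**4. Numbers for d = 0.5, 94 per arm.**
- 25% v 15%: difference 0.5 × 0.10 = 0.05 SD. Variances 0.75×1.25 − 0.375² = 0.797 and 0.85×1.25 − 0.425² = 0.882. SE = √((0.797+0.882)/94) = 0.134, and 0.05/0.134 = 0.374. Type I error = Φ(−1.96+0.374) + Φ(−1.96−0.374) = 0.066.
- 30% v 10%: difference 0.5 × 0.20 = 0.10 SD. Variances 0.7525 and 0.9225, SE 0.1335, ratio 0.749, type I error 0.116.

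| Common change | 25% v 15% | 30% v 10% |
|---|---|---|
| 0 | 0; 5% | 0; 5% |
| 0.25 SD | 0.025 SD; 5.4% | 0.05 SD; 6.7% |
| 0.5 SD | 0.05 SD; 6.6% | 0.10 SD; 11.6% |
| 1 SD | 0.10 SD; 10.8% | 0.20 SD; 29.0% |

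Simulation (20,000 trials per setting) agrees: 6.5% and 12.1% at 0.5 SD. If both sites recruited 94 per arm (188 in all), the 0.5 SD row becomes about 8% and about 18%.

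**5. Direction.** On a scale where higher is better, a common fall of 0.5 SD with 30% lost in SME+K and 10% in SME gives +0.10 SD for SME+K. A common rise of 0.5 SD gives −0.10 SD.

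**6. Equal drop-out.** At 20% in both arms a true difference of 0.40 SD is estimated as 0.80 × 0.40 = 0.32 SD, if drop-outs would have had the same benefit as completers.

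**7. Drop-out that is not random** (20% per arm, no common change or true effect, SME+K drop-out selective).
- Odds 2.7 times higher per SD of worse baseline: LOCF is biased by −0.07 SD with 8.4% type I error. A baseline-adjusted model gives 0.00 and 5.2%.
- Odds 2.7 times higher per SD of worse unseen change: LOCF is biased by +0.14 SD and the baseline-adjusted model by +0.13 SD.

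**8. Precision and power** (20% drop-out in both arms, no common change, true difference 0.40 SD, 94 per arm).

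| Analysis | SE | Interval width v LOCF | Power |
|---|---|---|---|
| LOCF, change score | 0.131 | reference | about 68% |
| LOCF, baseline-adjusted | not compared | not compared | about 76% |
| Likelihood model, arm means free at both times | 0.159 | 0.159/0.131 = 1.21 | about 70% |
| Baseline-adjusted, observed data | √(0.75×2/75.2) = 0.141 | 0.141/0.131 = 1.08 | 79–80% |

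**The case against.** The strongest reply is that every size here is assumed, and that mild assumptions give mild results. With a 10-point drop-out gap and a common change up to 0.5 SD, type I error is at most 6.6%. Adherence is a secondary objective, and section 4 promises cautious interpretation. This stands as a limit on severity, but caution in wording corrects neither a biased estimate nor a missing sensitivity analysis.

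Three further objections stand.
- **Baseline timing.** A reader might infer that every drop-out gets exactly zero change. That follows only if the section 3.4 session is the baseline. Reading (b) is less natural in a 2x2 design, but sections 2.1 and 3.1 do not exclude it. Under reading (a) the baseline falls after randomisation and possibly after the KARIE orientation in section 3.2.2, so adjusting for it could condition on something the allocation has already affected.
- **Target of estimation.** Calling 0.32 SD a shrunken 0.40 SD assumes that drop-outs would have benefited as completers did. If people who stop using the device lose its benefit, 0.32 SD could be close to the effect in everyone randomised.
- **Power.** A reader might infer from 68% v 79–80% that dropping LOCF buys about 12 points of power. It does not: baseline adjustment alone takes LOCF to about 76%, and the likelihood version of the planned test reaches only about 70%.

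A reader might also infer that LOCF would overwrite the observed 3-month scores of people who stopped the device but attended the visit. The rule's trigger, not finishing the intervention, is loose enough to allow this, but the text does not say so. It needs clarifying and is not a demonstrated error.

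**Conclusion.** The point holds for the repeated scales. The stated rule substitutes a pre-discharge score for a missing 3-month score, and the plan has nothing to test how much that matters. It should be fixed, but it is not a fatal flaw.

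Under the assumed common change of 0.5 SD, the false difference is 0.05 to 0.10 SD, with type I error of about 7% to 12% at West Park's 94 per arm. The sizes rest on assumed drop-out, change and correlation.

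The documents do not support two stronger conclusions. One is that LOCF would favour KARIE: the sign depends on which arm loses more people and which way scores drift, and neither is stated. The other is that the trial's type I error is inflated: with equal drop-out and no common change, and drop-out unrelated to baseline or outcome, there is no excess. The reason to drop LOCF is bias of unknown direction.

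**What to change.** Replace the LOCF sentence in section 4 with three statements.

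1. The 3-month scales are collected and analysed for every randomised participant, whether or not the intervention was completed. This also settles the loose trigger wording.
2. The 3-month score is compared between arms by a baseline-adjusted model: ANCOVA, or a likelihood-based repeated-measures model with a common baseline mean. Alternatively, multiple imputation using arm, site and baseline is followed by that model. The baseline must be measured before randomisation and before KARIE orientation, so sections 2.1, 3.1, 3.2.2 and 3.4 have to be reconciled on when it is taken.
3. Because item 2 is no safer than LOCF when drop-out depends on the unseen outcome, one sensitivity analysis shifts missing outcomes separately by arm and reports the shift at which the conclusion changes.

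The plan should also say which analysis track the satisfaction and acceptance questionnaire belongs to.

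The cost is analysis-plan wording and a little extra analysis; the 3-month visit is already scheduled. At 20% drop-out and no common change, the interval is about 8% wider than under LOCF with the baseline-adjusted model. It would be about 21% wider if the planned 2x2 test were refitted by likelihood with arm means free at both times, so the plan should name the model. The change should be made before outcome data are analysed by arm.

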Evaluation:	Yes	No	Initials	Date	Comments
Eligible for SMP (all 'yes' except for shaded boxes; *at the discretion of the team)					If not, name interventions:

SELF-MEDICATION PATIENT PERFORMANCE RECORD

LEVEL 1 (Minimum 48 hours) LEVEL 2 (Minimum 72 hours) Dosette Vial/Bottle Blister pack

START A NEW PAGE WHEN:

progressing a patient to a new level* AND/OR *when changing medication containers (dosette vs. blister back vs. bottle)

Date yy/mm/dd	Time	Initials/Designation	Time	Initials/Designation	Time	Initials/Designation	Time	Initials/Designation
Day no.  ____	 Independent  Physical assistance  Verbal cueing re: compartment  (Level 2): Cueing to initiate  Other: _____		 Independent  Physical assistance  Verbal cueing re: compartment  (Level 2): Cueing to initiate  Other: _____		 Independent  Physical assistance  Verbal cueing re: compartment  (Level 2): Cueing to initiate  Other: _____		 Independent  Physical assistance  Verbal cueing re: compartment  (Level 2): Cueing to initiate  Other: _____	

Date yy/mm/dd	Time	Initials/Designation	Time	Initials/Designation	Time	Initials/Designation	Time	Initials/Designation
Day no.  ____	 Independent  Physical assistance  Verbal cueing re: compartment  (Level 2): Cueing to initiate  Other: _____		 Independent  Physical assistance  Verbal cueing re: compartment  (Level 2): Cueing to initiate  Other: _____		 Independent  Physical assistance  Verbal cueing re: compartment  (Level 2): Cueing to initiate  Other: _____		 Independent  Physical assistance  Verbal cueing re: compartment  (Level 2): Cueing to initiate  Other: _____	

SELF-MEDICATION PATIENT PERFORMANCE RECORD

LEVEL 1 (Minimum 48 hours)
 LEVEL 2 (Minimum 72 hours)
 Dosette
 Vial/Bottle
 Blister pack

Date yy/mm/dd	Time	Initials/Designation	Time	Initials/Designation	Time	Initials/Designation	Time	Initials/Designation
Day no.  ____	 Independent  Physical assistance  Verbal cueing re: compartment  (Level 2): Cueing to initiate  Other: _____		 Independent  Physical assistance  Verbal cueing re: compartment  (Level 2): Cueing to initiate  Other: _____		 Independent  Physical assistance  Verbal cueing re: compartment  (Level 2): Cueing to initiate  Other: _____		 Independent  Physical assistance  Verbal cueing re: compartment  (Level 2): Cueing to initiate  Other: _____	

Date yy/mm/dd	Time	Initials/Designation	Time	Initials/Designation	Time	Initials/Designation	Time	Initials/Designation
Day no.  ____	 Independent  Physical assistance  Verbal cueing re: compartment  (Level 2): Cueing to initiate  Other: _____		 Independent  Physical assistance  Verbal cueing re: compartment  (Level 2): Cueing to initiate  Other: _____		 Independent  Physical assistance  Verbal cueing re: compartment  (Level 2): Cueing to initiate  Other: _____		 Independent  Physical assistance  Verbal cueing re: compartment  (Level 2): Cueing to initiate  Other: _____	

Date yy/mm/dd	Time	Initials/Designation	Time	Initials/Designation	Time	Initials/Designation	Time	Initials/Designation
Day no.  ____	 Independent  Physical assistance  Verbal cueing re: compartment  (Level 2): Cueing to initiate  Other: _____		 Independent  Physical assistance  Verbal cueing re: compartment  (Level 2): Cueing to initiate  Other: _____		 Independent  Physical assistance  Verbal cueing re: compartment  (Level 2): Cueing to initiate  Other: _____		 Independent  Physical assistance  Verbal cueing re: compartment  (Level 2): Cueing to initiate  Other: _____
